
Trial Manager and the research team’s qualified clinical psychologist has significant experience in working with distressed youth both in research and clinical settings. [name] is well equipped to oversee and manage any issues that may arise. All participants who receive a call back will be offered an additional follow-up call, scheduled 7 days after the initial call, to check-in about the agreed safety plan. In all instances, if a participant is unable to be contacted by phone after two attempts, they will be sent an email from the study email address informing them of the attempt to make contact. This email will also contain mental health information and support services.
 
c) A register of these events and associated interactions (i.e., telephone call attempts, times, dates, outcomes) will be recorded in a separate risk management spreadsheet managed by the Trial Manager. These events will also be recorded in the UNSW Safety Monitoring Template.
	
Effect/Event	Criteria

Severe depressive symptoms detected at final study assessment (i.e., secondary endpoint: 4-months post-baseline) through the self-report Patient Health Questionnaire-9.
	
A participant reports a total score ≥ 20 on the Patient Health Questionnaire-9 at secondary endpoint assessment (i.e., 4-months post-baseline).

Action	

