9. Do factors such as gender, age, baseline mental health history or symptom severity, openness to digital mental health, digital therapeutic alliance, perceived need for care, moderate the improvements in depressive symptoms found among users of *ClearlyMe*?
10. Do factors such as CBT skill acquisition, emotion regulation, rumination, and program engagement/completion mediate the improvements in depressive symptoms found among users of *ClearlyMe*?

Data

All participants will complete self-report questionnaires, including:

- Demographics (baseline only)
- Depressive symptoms (Patient Health Questionnaire: Adolescent version; PHQ-A; baseline, primary, secondary endpoints)
- Anxiety symptoms (Generalised Anxiety Disorder-7; GAD-7; baseline, primary, secondary endpoints)
- Psychological distress (Distress Questionnaire-5; DQ-5; baseline, primary, secondary endpoints)
- Emotional wellbeing (The Short Warwick-Edinburgh Mental Well-being Scale; SWEMWBS; baseline, primary, secondary endpoints)
- Perceived need and help-seeking barriers (Perceived Need for Care Questionnaire; PNCQ; baseline, primary, secondary endpoints)
- CBT skill acquisition (Cognitive Behavioural Therapy Skills Questionnaire; CBTSQ; baseline, primary, secondary endpoints)
- Quality of life (The Child Health Utility 9D; CHU-9; baseline, primary endpoints)
- Emotion regulation (Emotion Regulation Questionnaire for Children and Adolescents; ERQ-CA; baseline, primary, secondary endpoints)
- Rumination (Ruminative Response Scale; RRS-short form; baseline, primary, secondary endpoints)
- Digital therapeutic alliance (Digital Working Alliance Inventory; D-WAI; primary endpoint)
- Digital program satisfaction (Digital program satisfaction; Satisfaction Questionnaire; primary endpoint)
- Digital program barriers (Digital program barrier; Barriers Questionnaire; primary endpoint)
- Recent mental health care (Mental Health Care Questionnaire; primary endpoint)

Intervention use will be measured automatically for each digital intervention. Participants use of the *ClearlyMe* app will be measured by collecting data collected including lessons completed, collections completed, features accessed, total time spent in app, content liked/disliked, content saved, and individual responses to lesson activities.

Participants use of the psychoeducational content will be measured through Google analytics tracking the number of times the URL within the SMS is clicked on.

Trial Management Group (TMG)

Overview

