- Frequent, current suicidal ideation (i.e., thoughts of death or of harming oneself, score greater than 2 on item 9) detected through the self-report Patient Health Questionnaire-9 at primary or secondary endpoint.
- Severe depressive symptoms detected at final study assessment (i.e., secondary endpoint: 4-months post-baseline) through the self-report Patient Health Questionnaire-9.

- Mental health related hospitalisation reported at primary or secondary endpoint or disclosed in any other study procedures (e.g. call back phone calls, participant emails).
- Self-identified deterioration in mental health due to study activities reported by participants at primary or secondary endpoints.

Stopping guidelines

The primary charge of the TMG is to monitor the study for participant safety. As such, the TMG may recommend pausing or terminating the trial if they have concerns for participant safety, based on (but not limited to) a higher than anticipated rate for one or more of the primary endpoints.

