Appendix J: Standard operating procedures

The MobiliseMe study: Testing different smartphone activities to help improve young people's mental health

Trial Management Group

Version 1 (25th October 2021)

Procedures for eliciting reports of and for recording and reporting adverse event and intercurrent illnesses.

Adverse Events and Serious Adverse Events

For this current trial, an adverse event (AE) is defined as any untoward medical or clinical occurrence in a participant without regard to the possibility of a causal relationship. All AEs will be collected after a participant has consented and enrolled into the trial. AEs may include severe suicidal ideation as reported on baseline, primary or secondary endpoint online self-report assessment. Severe suicidal ideation will be defined as self-reports of suicidal thoughts or thoughts of self-harm More than half the days or Nearly every day, indicated by a score of ≥ 2 on item-9 of the PHQ-9. AEs also include severe depressive symptoms reported by participants at the final assessment (secondary endpoint) before trial ends. Severe depressive symptoms are indicated by a total score ≥ 20 on the Patient Health Questionnaire-9 at secondary endpoint assessment (i.e., 4-months post-baseline). Finally, AE also include mental health related hospitalisation reported at primary or secondary endpoint or disclosed in any other study procedures (e.g. call back phone calls, participant emails).

A serious adverse event (SAE) for this trial is defined as any untoward occurrence that involves hospitalization or death (suicide or otherwise) without regard to the possibility of a casual relationship.

Adverse Reactions (AR) are considered untoward and unintended responses to the trial intervention related to any intervention procedures. AR may include self-identified deterioration in mental health due to study activities reported by participants at primary or secondary endpoints.

Reporting Adverse Events

The trial will maintain a record of any reported adverse events or serious adverse events. A summary of adverse events will be reported to the trial's qualified expert (as named in Section 1). A summary of serious adverse events will be reported annually to the UNSW sponsors delegate and UNSW ethics committee.

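### A PHQ-A total of 20 or more is a primary safety endpoint only at 4 months, so some severe totals at the 6-week assessment meet no listed safety endpoint

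*Protocol*

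**What the plan says.** The restriction to 4 months is stated in three places.

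- Appendix I, Safety analyses: "Severe depressive symptoms detected at final study assessment (i.e., secondary endpoint: 4-months post-baseline".
- Section 11.1, Known Adverse Effects: "A participant reports a total score ≥ 20 on the Patient Health Questionnaire-9 at secondary endpoint assessment (i.e., 4-months post-baseline".
- Appendix J, adverse event definitions: "AEs also include severe depressive symptoms reported by participants at the final assessment (secondary endpoint) before trial ends".

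The same instrument is scheduled at all three assessments (Appendix I, Data: "PHQ-A; baseline, primary, secondary endpoints"), and its 6-week score is the primary outcome (sections 4 and 10). The other three primary safety endpoints in Appendix I are item 9 suicidal ideation, mental-health hospitalisation and self-identified deterioration. Each applies at 6 weeks and at 4 months.

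The TMG receives monthly safety reports and meets after each assessment wave. Its stopping guideline in Appendix I names "a higher than anticipated rate for one or more of the primary endpoints" as one ground for concern, expressly not the only one.

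**The concern.** Section 11.1 itself anticipates that CBT activities may cause a temporary rise in depressive and anxiety symptoms. Access to the interventions lasts 6 weeks, so the 6-week assessment is the one closest to exposure. A temporary rise seen then may have resolved by 4 months, which is the only time the severity endpoint is counted.

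The primary analysis does not fill the gap. The mixed model in section 10 estimates mean change, and a better mean can coexist with a minority who deteriorate. Section 13 plans no interim analysis of outcomes unless safety reports warrant one, so that model will not routinely inform the TMG during the trial. At stake is an incomplete comparison of harm between arms at the most informative time, in a trial where Appendix J makes the TMG the monitoring body in place of a data and safety monitoring committee.

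**Working it through.** No figure in the protocol needs reproducing. The check compares the safety definitions by time point, asks whether the endpoints that apply at 6 weeks can stand in for the missing one, and then sizes the gap.

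**Step 1. Definitions side by side (section 11.1, Appendices I and J).**

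| Primary safety endpoint | 6 weeks | 4 months | What triggers it |
|---|---|---|---|
| Suicidal ideation | yes | yes | item 9 score |
| Severe depressive symptoms | no | yes | total of 20 or more |
| Mental-health hospitalisation | yes | yes | self-report or disclosure |
| Self-identified deterioration | yes | yes | participant attributes worsening to study activities |

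Only the severe-symptom row differs by time point.

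**Step 2. Can the other rows substitute at 6 weeks?**

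- *Deterioration item.* It requires the participant to attribute the worsening to the study. The AE definition in Appendices I and J disregards causality, so this item is narrower.
- *Hospitalisation.* This is a much more extreme event than a severe total.
- *Item 9.* Assume nine items, each scored 0 to 3. With item 9 at 0 the other eight items can total 8 × 3 = 24; with item 9 at 1 the maximum is 25. A total of 20 or more is therefore possible below the item 9 threshold of 2. Enumerating all response patterns with a total of 20 or more gives 487 with item 9 at 0, 1,215 at 1, 2,643 at 2 and 5,115 at 3, which sum to 9,460. The patterns below the threshold number 487 + 1,215 = 1,702. These are counts of possible patterns, not probabilities.
- *A contradiction in the item 9 rule.* Section 11.1 and Appendix J set the threshold at 2 or more, whereas Appendix I says greater than 2. Read literally, the Appendix I wording would leave 1,702 + 2,643 = 4,345 of the 9,460 patterns uncaught. The passages need reconciling; the gap exists on either reading.

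**Step 3. Size.** Section 8 gives 489 randomised, 163 per arm, and 20% attrition to 6 weeks.

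- Assessed at 6 weeks: 489 × (1 − 0.20) = 391.2, about 391; per arm 163 × 0.80 = 130.4, about 130.
- The protocol gives no rate of severe totals, so the range of 2% to 15% is an assumption.
- At 2%: 391.2 × 0.02 = 7.8, about 8 in all (130.4 × 0.02 = 2.6, about 3 per arm).
- At 15%: 391.2 × 0.15 = 58.7, about 59 in all (130.4 × 0.15 = 19.6, about 20 per arm).

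These are participants outside the severity endpoint at 6 weeks. The number meeting no listed endpoint at all is smaller by an unknown amount.

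**Step 4. What does a 6-week total of 20 or more mean?** Sections 9.1 and 9.2 cap the score at 19 at screening. Section 9.5 then allows 14 days for parental consent and 7 days for the baseline assessment, 21 days together. No upper limit is re-applied at baseline, and the upper randomisation stratum in section 7 is simply 10 or more. A 6-week total of 20 or more is thus a rise since screening, but not necessarily since baseline.

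**The case against.** A reader might infer that worsening at the end of the intervention is never counted as harm. The protocol does not support that. Three of the four primary safety endpoints apply at 6 weeks, and one asks directly about worsening depression, anxiety or suicidality. The general AE definition has no time limit and Appendix J's list is worded inclusively, so a severe score at 6 weeks is not barred from being logged. It is just not listed.

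A reader might also infer that the TMG would not see deterioration at 6 weeks. That fails too: the stopping guideline is not limited to the listed rates, all AEs go to the TMG, and it meets after the 6-week assessments. It would see some deterioration, but not what shows only in the total score.

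Other points against the concern:

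- The 4-month event carries an end-of-study rationale: the call-back message in section 11.1 refers to the participant finishing the study. This explains the timing of the call-back. It does not explain leaving 6-week severe totals out of the count.
- Tables by arm and visit are ordinary SAP content, and the SAP is not at hand. That is fair for the table, but the endpoint's time point is fixed in the protocol itself.
- A total of 20 or more measures severity rather than change; a move from 19 to 20 is one point. This stands, and is why the baseline count belongs beside the later ones.
- The 20% attrition is stated only to 6 weeks. No 4-month figure is given, so losses between the two assessments cannot be sized from the protocol.

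**Conclusion.** The point holds in limited form. Score-defined severe depression is a primary safety endpoint at 4 months only, consistently in three places, although the score is available at 6 weeks. At 6 weeks, a severe total with item 9 below threshold, no hospitalisation and no self-attributed worsening meets no listed safety endpoint. If that participant is lost before 4 months, the severe total is never counted by score.

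The existence of the gap follows from the definitions and, for item 9, from assuming the 0 to 3 item scoring. Its size is not known from the protocol: about 8 to 59 of roughly 391 rests on the assumed 2% to 15% and is an upper figure for those missed altogether. The primary efficacy analysis is unaffected. The change should be made because it improves the detection of harm using data already held.

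**What to change.** 1. Extend the severe-symptom safety endpoint, for counting only, to the 6-week assessment. Make the same change in section 11.1, Appendix I and Appendix J; changing one alone would create a contradiction.
2. Tabulate by arm the number and proportion with a PHQ-A total of 20 or more at 6 weeks and at 4 months, with the baseline number alongside because the cap of 19 applies only at screening.
3. Include the 6-week count in the monthly TMG report, pooled over arms. The trial statistician is a TMG member (Appendix I) and is to remain blinded until the primary and secondary analyses are complete (section 7).
4. Reconcile the item 9 threshold between Appendix I and the other two places.

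No new data are needed. The cost is an amendment to three places, a few table rows and a higher recorded event count. If the 6-week scores are logged as AEs, section 11.2 adds reporting to the Coordinating Principal Investigator within 48 hours and, for those classed as not serious, assessment by the qualified physician; the amendment should say whether they are. Nothing here concerns the response to individual participants, which is for the sponsor to decide.

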
Participant instructions for use: In this trial, participants are provided with access to *ClearlyMe* for 6-weeks. Participants are instructed to complete the app content by undertaking at least one collection per week (approximately 20 minutes) for the intervention period; however, participants can complete the app content in any order and according to their preferences. Participants are also instructed to use the ‘Get Help’ section of the app if they feel they require extra mental health support during the intervention period, although this section of the app is not monitored in real-time by the research team. To further ensure compliance, all participants in this intervention arm will be sent one SMS per week from the Black Dog Institute Research Engine reminding them to use the *ClearlyMe* app. Participants allocated to this intervention arm will not receive any additional human

contact from the research team, unless technical support for the smartphone application (via email) is required.

Trial Arm 2. Intervention 2 – Guided use of CBT smartphone application *ClearlyMe*: Participants allocated to this condition will receive the same intervention provided in Trial Arm 1, with the addition of a weekly guided support session. This will take place in the form of a SMS chat provided by the research team for the duration of the intervention period. Participants will be contacted via SMS on their mobile phone number at the times provided to participants after randomisation (4pm to 7pm Monday to Friday). Contact will be made weekly, with one additional attempt made for non-response (two days apart, total of 2 contact attempts in 7 day period). In total, participants in this condition will receive 6 weekly support sessions in the intervention period. Personnel conducting the guided sessions will be research employees of the Black Dog Institute and will use a standard script, with a decision flow chart to direct the chat (see Appendix F). The SMS chat will consist primarily of technical support with some low intensity motivational coaching. Research Assistants (RAs) not clinicians, will be trained to conduct these sessions and will be supervised by a clinician. The clinician will be available during these sessions to support the RA if needed. The guided support sessions will be designed to be conducted in one sitting (i.e., within 20 minutes) but duration and script compliance will be recorded by the research assistants.

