Participant instructions for use: In this trial, participants are provided with access to *ClearlyMe* for 6-weeks. Participants are instructed to complete the app content by undertaking at least one collection per week (approximately 20 minutes) for the intervention period; however, participants can complete the app content in any order and according to their preferences. Participants are also instructed to use the ‘Get Help’ section of the app if they feel they require extra mental health support during the intervention period, although this section of the app is not monitored in real-time by the research team. Participants will be instructed that they can expect a weekly SMS chat for the duration of the study period any time between the hours of 4pm to 7pm Monday to Friday.

Trial Arm 3. Active attention-matched control – SMS enabled, self-directed low intensity weekly psycho-education flyers with self-care:

This study will utilise an active attention matched control condition. Participants allocated to this condition will receive 6 weekly psychoeducation modules delivered via SMS with handouts that can be accessed on their mobile device. The psycho-education consists of 6 topics: What is mental health, Feeling on Edge – Understanding Anxiety, Waves of Sadness – Understanding Depression, When it’s time to tell someone, When a friend needs a hand, and When friendships are complicated. Each module consists of information about mental health problems, links to credible Australian mental health organisations, and finishes with selfcare suggestions for what a young person can do right now if they are feeling worried or down. These modules were developed by the Black Dog Institute, created by mental health professionals, researchers and young people. Each module takes approximately 20 minutes to complete. A full overview of the psychoeducation content is provided as in Appendix G. Participants allocated to this intervention arm will not receive any additional human contact from the research team, unless technical support for the program (via email) is required. At the primary endpoint, participants will receive one email that contains all of the psycho-education material in one collated document for future use.

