

is unable to be contacted by phone after two attempts, they will be sent an email from the study email address informing them of the attempt to make contact. This email will also contain mental health information and support services.
 
c) A register of these events and associated interactions (i.e., telephone call attempts, times, dates, outcomes) will be recorded in a separate risk management spreadsheet managed by the Trial Manager. These events will also be recorded in the UNSW Safety Monitoring Template.
	
Effect/Event	Criteria

Mental health related hospitalisation reported at primary or secondary endpoint or disclosed in any other study procedures (e.g. call back phone calls, participant emails).
	
Participants reports yes to the item “Throughout the study, have you had any mental health problems where you had to go to a hospital emergency department, or had to stay in hospital for more than one day?” in the primary and secondary endpoint study assessments, or, reports this event via other study procedures and activities.

Action	

All relevant study data for this event will be recorded in the UNSW Safety Monitoring Template for reporting.
	
Effect/Event	Criteria

Self-identified deterioration in mental health due to study activities reported by participants at primary or secondary endpoints.
	
Participants reports yes to the item “At any point throughout the study, did you feel that any of the study activities made your mental health or feelings of depression, anxiety or suicidality worse?” in the primary and secondary endpoint assessments, or, reports this event via other study procedures and activities.

Action	

All relevant study data for this event will be recorded in the UNSW Safety Monitoring Template for reporting.
	

b) Known Harms, Risks or Discomforts

The interventions evaluated in this trial have been designed and reviewed by mental health professionals to support young people to manage their mental health. The researchers do not anticipate significant harm or distress related to use of the interventions in the current trial, however, the following harms, risks or discomforts may occur:

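### The hospitalisation safety endpoint also counts events disclosed outside the surveys, and only the guided arm has scheduled staff contact, so missed events can surface more often there; the deterioration definitions also conflict

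*Protocol*

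**What the plan says.** **Hospitalisation.** Appendix I (Safety analyses) lists as a primary safety endpoint "Mental health related hospitalisation reported at primary or secondary endpoint or disclosed in any other study procedures", naming call-back calls and participant emails as examples. Section 11.1 and Appendix J carry the same open route.

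**Self-identified deterioration.** The criterion in Section 11.1 is a yes answer "in the primary and secondary endpoint assessments, or, reports this event via other study procedures and activities". Appendix I has only "Self-identified deterioration in mental health due to study activities reported by participants at primary or secondary endpoints", and Appendix J has the same restriction. Section 11.1 is also at odds with itself: its event description names the two endpoints only, and its criterion then widens them.

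**Staff contact by arm (Section 10.1).**
- Arm 2 (guided): "In total, participants in this condition will receive 6 weekly support sessions in the intervention period". These are SMS chats run by trained research assistants with a clinician available. A second attempt is made in the week if there is no reply.
- Arm 3 (control): "Participants allocated to this intervention arm will not receive any additional human contact from the research team", apart from technical support by email.
- Arm 1 (self-directed): the same restriction. Its weekly SMS is an automated reminder.

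**Use of the endpoints.** Appendix I gives the Trial Management Group (TMG) a monthly safety report, sends it both solicited and spontaneous adverse events, and allows it to recommend pausing or terminating the trial when a safety endpoint occurs more often than anticipated.

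**The concern.** An endpoint met by a survey answer or by any other disclosure is only as comparable between arms as its less equal route. The survey route is the same for everyone. The other route is not: in Arm 2 a staff member opens a conversation every week, whereas in Arms 1 and 3 the participant must start one or trigger a call-back through an assessment. Equal true rates can then produce unequal recorded rates, with the excess in the guided arm.

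Timing is affected too. The solicited items are first asked at week 6, but chats run from randomisation to week 6, so an Arm 2 event can enter a monthly TMG report earlier than a similar event elsewhere. This part does not depend on survey attrition.

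At stake is how any by-arm safety table is read in a trial that sets guided against self-directed use in adolescents. The conflicting definitions of deterioration add a second problem: the same disclosure counts under Section 11.1 but not under Appendix I.

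**Working it through.** **Definitions side by side**

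| Event | Section 11.1 | Appendix I | Appendix J |
|---|---|---|---|
| Hospitalisation | surveys or other procedures | surveys or other procedures | surveys or other procedures |
| Deterioration | event description: surveys; criterion: surveys or other procedures | surveys only | surveys only |

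Hospitalisation has the open route throughout. Deterioration has it only in the Section 11.1 criterion.

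**Inputs**
- From the protocol (Section 8): 163 participants per arm; 20% attrition by the primary endpoint.
- Not in the protocol, so assumed: the true event rate, the share of events captured by routes open to all arms (*a*), and the share of the remaining events that surface in guided chats (*c*). The plan has no figure of its own on this point to reproduce.

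**Formula.** With equal true rates, Arms 1 and 3 record a fraction *a* of events and Arm 2 records *a* + (1 − *a*)*c*, so the detection ratio is

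(*a* + (1 − *a*)*c*) / *a*.

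**Values of *a*.** Take an event before week 6 and full reporting by those who answer.
- If no one who misses the week-6 survey returns the second, *a* = 1 − 0.20 = 0.80.
- If the second survey is missed independently with the same probability (an assumption), *a* = 1 − 0.20 × 0.20 = 0.96.

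| *a* | *c* = 0.25 | *c* = 0.5 | *c* = 1 (maximum) |
|---|---|---|---|
| 0.96 | 0.97/0.96 = 1.01 | 0.98/0.96 = 1.02 | 1.00/0.96 = 1.04 |
| 0.80 | 0.85/0.80 = 1.06 | 0.90/0.80 = 1.13 | 1.00/0.80 = 1.25 |

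If survey completers also failed to report 20% of events, *a* = 0.80 × 0.80 = 0.64 and the ratios would be 0.73/0.64 = 1.14, 0.82/0.64 = 1.28 and 1.00/0.64 = 1.56. Nothing in the protocol points to under-reporting of that size, so this is a sensitivity case and not part of the main range.

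**In events**, at an assumed true rate of 5%:
- *a* = 0.80, *c* = 0.5: Arm 2 records 163 × 0.05 × 0.90 = 7.3; each other arm 163 × 0.05 × 0.80 = 6.5.
- *a* = 0.96, *c* = 0.25: 163 × 0.05 × 0.97 = 7.9 against 163 × 0.05 × 0.96 = 7.8.

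The gap is therefore between about 0.1 and 0.8 of an event per arm in these two cases.

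**Dilution.** The chats end with the 6-week intervention period. Events between week 6 and 4 months can be picked up only by the second survey and the shared routes, so they add no imbalance and pull the overall ratio towards 1.

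**After the fix.** Counting solicited items only sets *c* = 0, and the ratio is 1.00, provided survey response is similar across arms.

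**The case against.** The case against has real force.

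- **The main routes are shared.** Both items look back over the whole study and are asked twice in every arm. The examples that Appendix I names, call-backs and emails, are open to all. So are contacting the team in distress (Section 11.1) and reporting adverse events at withdrawal (Section 9.6). A reader might infer that events outside the surveys are lost in Arms 1 and 3; the documents do not support that. What remains is narrower: call-backs are triggered by answers in an assessment, so someone who skips both follow-up surveys must make contact unprompted in Arms 1 and 3 but is approached in Arm 2.
- **The chats may not elicit harms.** Section 10.1 describes them as mainly technical support with light motivational coaching, and the script (Appendix F) is not available here. A reader might infer that harms *will* be found more often in Arm 2; the text supports only that they *can* be. The second weekly attempt follows non-response, so it does not double the number of conversations.
- **No between-arm safety test is specified.** The stopping guideline refers to a higher rate than anticipated, not to a contrast between arms, and tabulation may be left to the analysis plan. This stands, but the endpoint definition is fixed in the protocol, and any table by arm inherits it.
- **Solicited-only counting could hide a known hospitalisation.** This stands against a fix that drops other disclosures. It does not apply if an all-source total is shown alongside.

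**Conclusion.** The point holds in limited form. The protocol's hospitalisation endpoint, and deterioration as Section 11.1 states it, give the guided arm more opportunity for detection than the other two. The direction follows from the design for any disclosure share above zero. The size cannot be known from the documents and is probably small: a ratio of about 1.01 to 1.25 with equal true rates, 20% attrition, and assumed capture of 80% to 96% by the shared routes. A larger ratio would need substantial under-reporting by survey completers as well.

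Two stronger readings should be avoided. One is that Appendix I opens both endpoints to outside disclosure; it does so for hospitalisation only, and the conflict with Section 11.1 on deterioration must be reconciled whatever is decided about detection. The other is that the imbalance undermines the aim in Section 4 of examining delayed harms; that aim is tied to self-report scales given identically in all arms.

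This is a cheap improvement to how harms are counted and shown, not a flaw that threatens the trial's conclusions.

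**What to change.** 1. Reconcile the definition of self-identified deterioration across Section 11.1 (event description and criterion), Appendix I and Appendix J.
2. In Section 11.1 and Appendix I, state that any between-arm comparison of hospitalisation and deterioration uses the solicited items asked identically in all arms, with the number answering given per arm. Those denominators matter because solicited-only counting does not correct for unequal survey response.
3. Add a source field to the safety register (survey, SMS chat, call-back, email, withdrawal report, other). Report disclosures from outside the surveys by arm and source, next to an all-source total, so that no known hospitalisation is left out of the safety report or TMG review. Showing the source in the monthly reports also lets the TMG see when an early excess comes from the chats.

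The cost is a sentence in each of the two sections, one register column and one more table. The downside is that the solicited-only comparison counts slightly fewer events. Recording and safety follow-up of events are unchanged.
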